5.0 STUDY FLOW CHART

Trial Period:	Screening Phase	Treatment Cycles ^j								End of Treatment	Post-Treatment		Survival Follow Up ^k	
		1	2	3	4	5	6	7	8		If pt returns for follow up	Safety F/U ^f	Follow-Up ^g	
Treatment Cycle/Title:	Screening /Baseline									Cycle 9 and beyond				
Scheduling Window (Days):	Within 28 days	± 3	± 3	± 3	± 3	± 3	± 3	± 3	± 3			1 month after last dose	3 months after last dose	Annually for at least 5 years
Informed Consent	x													
Inclusion/Exclusion Criteria	x													
Demographics and Breast Cancer History ^a	x													
Concomitant Medication Review per SOC	x													
Physical Exam ^b , V/S	x	x	x	x	x	x	x	x	x	x	x			
Adverse Events ^b	x	x	x	x	x	x	x	x	x	x	x	x	x	
ECOG Performance Status ^b	x	x	x	x	x	x	x	x	x	x	x			
Pregnancy Test – Urine or Serum β-HCG (for women with childbearing potential)	x													
CBC and Biochemical Profiles ^c	x	x	x	x	x	x	x	x	x	x	x			
EKG, ECHO or MUGA as SOC ^d	x													
TSH, Free T4 and Totalcortisol ⁱ	x		x		x		x		x	x	x			
Radiological Evaluation as clinically indicated and as SOC ^d	x		x		x		x		x	x	x			
Archived biopsy or surgical specimens (block or unstained slides) obtained at any time prior to treatment.	x													
Correlative Studies Blood Collection ^e	x		x		x		x		x	x				
MK-3475 Administration		x	x	x	x	x	x	x	x	x				
Survival Status												x	x	
Optional biopsy at disease progression ^h											x			

- Demographics include patient's age, gender and race. Medical history includes primary breast cancer pathological diagnosis, ER/PR/HER2 status, and metastatic disease sites. prior therapies and procedures for breast cancer,
- Complete physical exam during the screening period. This will not be repeated if done within 8 (+/- 3 days) days before the start of treatment. During treatment, Physical Exam as clinically indicated prior to trial treatment administration. Adverse events and ECOG performance status assessment can be done within 8 (+/- 3 days) days before the start of treatment. Adverse events and ECOG will be assessed every 3 weeks either in the clinic visit or by calling through the end of treatment.
- Hematologic and biochemical profiles (CBC, albumin, alkaline phosphatase, ALT, AST, LDH, uric acid, calcium, glucose, phosphorus, potassium, sodium, magnesium, total bilirubin, total protein,

BUN, as standard of care (will not be repeated if done within 8 (+/- 3 days) days before the start of treatment). During treatment, an earlier evaluation will be performed if clinically indicated.

- d. Radiological evaluation may include CT of the chest and abdomen, Ultrasound, bone Scan and X-Rays, brain MRI as clinically indicated for standard of care. PET/CT, Chest wall/breast photos, EKG and ECHO or MUGA may also be performed as indicated for standard of care. During treatment, an earlier evaluation will be performed if clinically indicated. The same method of evaluation, specific to the subject's condition, will be performed according to the time points.
- e. Peripheral blood and serum for correlative studies. Approximately 50cc of blood will be drawn at baseline, cycle 3rd, 6th, 9th, then every 2 cycles (i.e.11th, 13th, 15th, etc.) and at disease progression.
- f. The mandatory Safety Follow-Up Visit should be conducted approximately 30 days after the last dose of trial treatment or before the initiation of a new anti-cancer treatment, whichever comes first. All AEs that occur prior to the Safety Follow-Up Visit should be recorded. Safety Follow-Up Visit can be done in the clinic, or by phone if patient is not willing to come to the clinic for follow up.
- g. 3 months follow up can be performed in the clinic, or by phone if patient is not willing to come to the clinic for follow up.
- h. Optional biopsy at disease progression.
- i. TSH, Free T4 and Total cortisol will be monitored at baseline, every other cycle during Cycle 1-8 and every cycle for Cycle 9 and beyond as standard of care.
- j. Cycle 1-8 are defined as 3 weeks per cycle, Cycle 9 and beyond are defined as 6 weeks per cycle, pembrolizumab (200mg or 400mg) will be given on Day 1 of each cycle as section 4.2.
- k. registration

6.0 OTHER STUDY PROCEDURES

6.1 Informed Consent/Patient Registration

The study will be discussed with the patient, and any patient wishing to participate must give informed consent. A signed, Institutional Review Board (IRB) approved, informed consent must be obtained from patients before any study specific procedures or registration for study treatment can occur. All patients will be registered in the OnCore system.

6.2 Biomarker assessments

Tumor tissue and peripheral blood will be collected prior to therapy and at selected time points on treatment. Residual sample material available after completion of the designated analyses may be used in the future for identification of additional predictive markers or to enhance understanding of disease biology. If biomarker samples are drawn but study drug is not administered, samples will be retained. A description of each assay system is described below.

6.2.1 Tumor Samples

Collection

Archived biopsy or surgical specimens (block or unstained slides) obtained at any time prior to treatment will be collected from all consenting subjects. Optional biopsies will be obtained from patients with disease progression and accessible lesions.

Evaluation

- Characterization of tumor infiltrating lymphocytes (TIL).
- Immunohistochemistry (IHC) will be used to assess the immune infiltrates in order to define the immune cell subsets present within formalin-fixed, paraffin-embedded tumor tissue. These IHC analyses will include but not necessarily be limited to: CD4, CD8, FOXP3, PD-1, and PD-L1. PD-L1 IHC will be performed by both MD Anderson and QualTek.
- Genetics profiling performed by Insight Genetics (only done for the prior biopsy and/or surgery tumor samples).

6.2.2 Blood samples

Collection and processing

Multiple blood draws will be required for this trial. All blood tubes will be labeled only with the patients' unique study number. Approximately 100cc will be drawn for each immunologic assessment (at baseline; prior to dosing of study drug with every third cycle i.e. cycle 3, 6, 9, 12 etc , or every other cycle after for patients who start Pembrolizumab 400mg at C9 and beyond; and at disease progression). 10cc will be collected into a BD Vacutainer Rapid Serum tube (BD, Franklin Lakes, NJ) which contains a clot activator and silicone coated interior. After

centrifugation, serum will be collected, aliquoted in 1cc vials and frozen. 70cc will be collected into BD Vacutainer CPT Cell Preparation tubes which contain an anticoagulant (sodium heparin or sodium citrate) with FICOLL HYPAQUE density gradient fluid and a polyester gel barrier. The density gradient fluid and the gel barrier allow for the separation of peripheral blood mononuclear cells (PBMC) from the red blood cells by a single step centrifugation process. The PBMC fraction will be collected by centrifugation and suspended in RPMI-1640 (GIBCO, Invitrogen Corporation, Carlsbad, CA) with 10% FCS (Gemini Bio-Products, West Sacramento, CA) and antibiotics. Plasma will be collected from CPT Cell Preparation tubes and stored. 20cc blood will be collected in heparin 10ml green top tubes for FACS assay.

6.2.3 Assays

Serum

- Soluble factors such as cytokines and chemokines present in serum collected at baseline, during, and after treatment will be quantified using a multiplex assay which has the capability to simultaneously measure multiple analytes from a single sample. Factors to be evaluated may include but not necessarily be limited to IFN- γ , TNF- α , IL-2, IL-4, IL-5, IL-7, IL-10, IL-12, IL-15 and IL-17.
- Additional immunoassays will be performed to quantify soluble receptors present in the serum. Analyses may include but not necessarily be limited to soluble CD25, soluble PD-1, and soluble LAG-3.

Peripheral blood mononuclear cells

- The proportion of specific lymphocyte subsets to include T cells, B cells, and the proportion of memory and effector T cell subsets will be quantified by flow cytometry.
- The expression levels of T cell co-stimulatory and co-inhibitory markers including but not necessarily limited to PD-1, PD-L1, other B7 family members, and ICOS will be quantified by flow cytometry.

Plasma

- Exosomal RNA-sequencing will be performed with RNA extracted from plasma by Insight Genetics, Inc along with the tumor sample listed in section 6.2.1. There is only one time point plasma sample needed, and plasma samples at baseline will be preferred, but samples collected at other time points can be substitute if the baseline sample is unavailable.
- Plasma will be stored for future research purpose.

FACS assay

- Intracellular cytokine synthesis by T-cells activated through the T-cell receptor (TCR).
- Cytokine production by dendritic cells activated with Toll-like receptor (TLR) agonist.

- The NK cell assay.

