2.2 Exploratory Objective

- (1) To investigate the association between biomarkers in the peripheral blood and tumor tissue, such as PD-L1 expression, with safety and efficacy for IBC or non-IBC TNBC patients treated with MK-3475.
- (2) To determine the disease control rate of metastatic IBC or non-IBC TNBC patients who have achieved clinical response or stable disease to the systemic therapy.
- (3) To investigate the association between biomarkers and efficacy by RNA-sequencing of exosomes in blood and tumor for IBC or non-IBC TNBC patients treated with MK-3475.
- (4) To investigate the 5-year OS for IBC or non-IBC TNBC patients treated with MK-3475

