Various biomarker endpoints will be measured in various specimens. Correlation among biomarkers at baseline in each specimen and between different specimens will be assessed. The association among various continuous and discrete biomarkers or disease status groups will be assessed by the exploratory data analysis using scatter plot matrix, box plots, BLIP plot³⁷ and trellis plot, etc, and may be tested by t-test/ANOVA/Wilcoxon rank sum test/Kruskal-Wallis test, whichever is appropriate. Correlation between continuous biomarkers will be examined by Pearson or Spearman rank correlation coefficients. The association between discrete biomarkers will be tested by chi-square or Fisher's exact test. Paired t-test/Wilcoxon rank sum test and McNemar's test may be used to test the change of a single continuous biomarker and discrete biomarker, respectively, over time within each treatment group. Repeated measures analysis including mixed effects model will be performed to analyze the correlation between disease control and biomarkers change over time.³⁸ Disease control survival and overall survival time from the registration date will be estimated using Kaplan-Meier method.

All statistical tests will be performed at a two-sided significance level of 5% using SAS or S-Plus, as appropriate.

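### Exosome RNA and efficacy: a missing baseline plasma sample may be replaced by one from any later time point, which can bias the association if substitution occurs and RNA changes on treatment or at progression

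*Combined protocol and SAP*

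**What the plan says.** Section 2.2 sets exploratory objective (3): "To investigate the association between biomarkers and efficacy by RNA-sequencing of exosomes in blood and tumor", in the patients treated with MK-3475.

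Section 6.2.3 describes the plasma assay: "There is only one time point plasma sample needed, and plasma samples at baseline will be preferred", and then "samples collected at other time points can be substitute if the baseline sample is unavailable". It sets no limit on how late a substitute may be and excludes no type of draw.

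The available time points come from two places. Footnote e of the Section 5.0 flow chart has blood "drawn at baseline, cycle 3rd, 6th, 9th, then every 2 cycles" "and at disease progression". Section 6.2.2 lists baseline and every third cycle, "or every other cycle after for patients who start Pembrolizumab 400mg at C9 and beyond; and at disease progression". It also says of the tubes filled at each such draw: "Plasma will be collected from CPT Cell Preparation tubes and stored". Progression draws therefore yield plasma too.

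Section 7.0 measures disease control at 4 months from the start of therapy. Its biomarker paragraph has no landmark rule, no adjustment for sampling time, no flag for substituted samples and no baseline-only sensitivity analysis.

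**The concern.** A predictor measured before treatment has the same meaning in every patient. Here, for a patient without a baseline sample, the predictor may be measured on treatment, at progression, or after the outcome has been determined. The substitute a patient can supply is linked to outcome. A patient who progresses early can offer only an early on-treatment draw or a progression draw. A patient who stays on treatment can offer cycle 6, cycle 9 or later.

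If exosomal RNA changes with treatment or with progression, that change enters the predictor unevenly between controlled and non-controlled patients. A transcript with no baseline association could then look like a marker of efficacy, or a real association could be distorted. What is at stake is the plasma half of one exploratory objective.

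**Working it through.** **Timing.** Cycles 1 to 8 last 3 weeks and later cycles 6 weeks (Sections 4.2.1 and 5.0). Day 1 of cycle k, for k up to 9, falls at 3 × (k − 1) weeks.

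- Cycle 3: 3 × 2 = week 6
- Cycle 6: 3 × 5 = week 15
- Cycle 9: 3 × 8 = week 24
- Cycle 11: 24 + 2 × 6 = week 36
- Outcome at 4 months: 4 × 30.4375 / 7 = week 17.4

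Cycle 3 and 6 samples are on treatment but precede the outcome. Cycle 9 and later samples follow it and come from patients still on treatment. A progression draw before week 17.4 comes from a patient judged to have progressed before the endpoint. A progression draw after it may come from a patient who was controlled at 4 months.

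**Expected spurious difference.** The plan gives no figure to reproduce, so all inputs here are assumptions. Let f be the share of baselines missing (at random) and substituted, and s the shift in SD units of a shifted sample. Let a and b be the fractions of substitutes that are shifted among non-controlled and controlled patients. With no true baseline association, the expected difference between groups is f × s × (a − b).

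- Extreme, a = 1, b = 0: f = 0.20 and s = 1 give 0.20 SD; s = 2 gives 0.40 SD.
- Half of non-controlled shifted, a = 0.5, b = 0: 0.20 × 1 × 0.5 = 0.10 SD; s = 2 gives 0.20 SD.
- A quarter of controlled shifted as well, a = 0.5, b = 0.25: 0.20 × 1 × 0.25 = 0.05 SD; s = 2 gives 0.10 SD.
- a = b, or f = 0: zero.

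**False-positive rate.** This was simulated per marker, with a two-sided 5% test and no true baseline association. Ranges run from s = 1 to s = 2.

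| Share substituted | Extreme, n = 50 | Half of non-controlled shifted, n = 50 | Plus a quarter of controlled, n = 50 |
|---|---|---|---|
| 0% | about 0.05 | about 0.05 | about 0.05 |
| 10% | 0.05–0.07 | not tabulated | not tabulated |
| 20% | 0.08–0.15 | 0.05–0.07 | 0.05–0.06 |
| 30% | 0.12–0.27 | 0.06–0.10 | 0.05–0.06 |

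Section 7.0 pairs 50 patients with a 25% target and 35 patients with a 30% target. The extreme case with those pairings, by t-test:

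| Share substituted | n = 50, 25% controlled | n = 35, 30% controlled |
|---|---|---|
| 10% | 0.050–0.062 | 0.051–0.057 |
| 20% | 0.075–0.130 | 0.072–0.100 |
| 30% | 0.114–0.244 | 0.103–0.194 |

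These rates come from 6,000 trials per setting, so the simulation standard error near 0.05 is √(0.05 × 0.95 / 6000) = 0.003. Of 50 patients, 10%, 20% and 30% substituted means 5, 10 and 15 patients.

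**The case against.** The strongest reply is that this is an exception clause in an exploratory objective. A baseline draw is scheduled for every patient, baseline is preferred, and no missing rate is given. If every baseline sample exists, nothing happens. That stands, and it is why the bias is stated as conditional.

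The size also depends on a one-sided setup. Cycle 3 is drawn from everyone still on treatment, so a patient who fails between week 6 and month 4 can also have a pre-progression sample. With treatment of up to 24 months (Section 4.5.6), a patient controlled at month 4 can progress later and give a progression draw. Both facts narrow the gap between groups, and the milder columns of the first table show how much. That stands too.

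Three stronger readings are tempting. First, a reader might infer that the rule certainly biases the result. The documents do not show that any baseline is missing or that RNA shifts. Second, a reader might infer that a progression sample marks a 4-month failure. It does so only if drawn before month 4. Section 6.2.3 does not name progression samples either; they are admitted by its unrestricted wording. Third, a reader might extend the point to the repeated-measures model, meant "to analyze the correlation between disease control and biomarkers change over time". That does not follow. Exosome RNA needs one time point only, the model seeks a longitudinal association rather than baseline prediction, and cutting its data at cycle 6 would discard planned samples.

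What the reply does not answer is that substitution is expressly allowed without limit, and nothing in Section 7.0 handles it.

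**Conclusion.** The substitution rule in Section 6.2.3 leaves the exosome–efficacy association open to bias tied to the patient's course, and the plan has no safeguard. The bias arises only if some baselines are missing and exosomal RNA changes with treatment or progression differently in the two outcome groups. Neither quantity is in the documents.

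On assumed values the inflation is slight at 10% substitution even in the extreme case. At 20% to 30% it becomes material only when the shift falls mainly on non-controlled patients; otherwise it stays at about 0.05–0.10. The unlimited substitution rule is certain; the size of its effect is not.

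The primary endpoint, sample size and stopping rules are unaffected. So is the tumor half of objective (3), because Section 6.2.1 limits genetic profiling to earlier biopsy or surgical specimens. No change to the repeated-measures model is called for.

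**What to change.** In Section 6.2.3, restrict the exosome RNA association with efficacy to plasma drawn before the first dose. Report patients who have only later plasma separately and descriptively, with the sampling time recorded. State that a sample taken at progression may not stand in for baseline.

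This takes a sentence or two and no new assay or visit. The cost is that patients without baseline plasma leave this exploratory analysis, which loses some precision. Their later samples cannot establish a baseline association, and they remain available for description.

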6.3 Safety Monitoring and Reporting

6.3.1 Adverse Event

Adverse events will be assessed according to the CTCAE version 4.0. All study patients who have received any dose of MK-3475 will be evaluable for safety. Unexpected adverse events including laboratory adverse events deemed clinically significant by the investigator will be graded and recorded.

The ongoing review of safety data will include review of clinical AEs and SAEs. The NCI-CTC version 4.0 will be used to grade all AEs.

AEs ($>/=2$ non-hematological and $>/=3$ hematological AEs) occurring after informed consent signing observed by the investigator or reported by the subject (whether or not attributed to investigational product), will be documented in the medical record and recorded in REDCap database. Abnormal laboratory values will not be reported as AEs; however, any clinical consequences of the abnormality should be reported as AEs.

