4.2.2 Dose Modification

Adverse events (both non-serious and serious) associated with pembrolizumab exposure may represent an immunologic etiology. These adverse events may occur shortly after the first dose or several months after the last dose of treatment. Pembrolizumab must be withheld for drug-related toxicities and severe or life-threatening AEs as per Table 2 below. See Section 4.4 and Events of Clinical Interest Guidance Document for supportive care guidelines (Appendix C), including use of corticosteroids.

Table 2 Dose Modification Guidelines for Drug-Related Adverse Events

Toxicity	Hold Treatment For Grade	Timing for Restarting Treatment	Treatment Discontinuation
Diarrhea/Colitis	2-3	Toxicity resolves to Grade 0-1.	Toxicity does not resolve within 12 weeks of last dose or inability to reduce corticosteroid to 10 mg or less of prednisone or equivalent per day within 12 weeks.
	4	Permanently discontinue	Permanently discontinue
AST, ALT, or Increased Bilirubin	2	Toxicity resolves to Grade 0-1	Toxicity does not resolve within 12 weeks of last dose.
	3-4	Permanently discontinue (see exception below) ¹	Permanently discontinue
Type 1 diabetes mellitus (if new onset) or Hyperglycemia	T1DM or 3-4	Hold pembrolizumab for new onset Type 1 diabetes mellitus or Grade 3-4 hyperglycemia associated with evidence of beta cell failure.	Resume pembrolizumab when patients are clinically and metabolically stable.
Hypophysitis	2-4	Toxicity resolves to Grade 0-1. Therapy with pembrolizumab can be continued while endocrine replacement therapy is instituted	Toxicity does not resolve within 12 weeks of last dose or inability to reduce corticosteroid to 10 mg or less of prednisone or equivalent per day within 12 weeks.
Hyperthyroidism	3	Toxicity resolves to Grade 0-1	Toxicity does not resolve within 12 weeks of last dose or inability to reduce corticosteroid to 10 mg or less of prednisone or equivalent per day within 12 weeks.
	4	Permanently discontinue	Permanently discontinue
Hypothyroidism		Therapy with pembrolizumab can be continued while thyroid replacement therapy is instituted	Therapy with pembrolizumab can be continued while thyroid replacement therapy is instituted.

Toxicity	Hold Treatment For Grade	Timing for Restarting Treatment	Treatment Discontinuation
Infusion Reaction	3-4	Permanently discontinue	Permanently discontinue

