Pneumonitis	2	Toxicity resolves to Grade 0-1	Toxicity does not resolve within 12 weeks of last dose or inability to reduce corticosteroid to 10 mg or less of prednisone or equivalent per day within 12 weeks.
	3-4	Permanently discontinue	Permanently discontinue
Renal Failure or Nephritis	2	Toxicity resolves to Grade 0-1	Toxicity does not resolve within 12 weeks of last dose or inability to reduce corticosteroid to 10 mg or less of prednisone or equivalent per day within 12 weeks.
	3-4	Permanently discontinue	Permanently discontinue
All Other Drug-Related Toxicity ²	3 or Severe	Toxicity resolves to Grade 0-1	Toxicity does not resolve within 12 weeks of last dose or inability to reduce corticosteroid to 10 mg or less of prednisone or equivalent per day within 12 weeks.
	4	Permanently discontinue	Permanently discontinue

Note: Permanently discontinue for any severe or Grade 3 drug-related AE that recurs or any life-threatening event.

¹ For patients with liver metastasis who begin treatment with Grade 2 AST or ALT, if AST or ALT increases by greater than or equal to 50% relative to baseline and lasts for at least 1 week then patients should be discontinued.

² Patients with intolerable or persistent Grade 2 drug-related AE may hold study medication at physician discretion. Permanently discontinue study drug for persistent Grade 2 adverse reactions for which treatment with study drug has been held, that do not recover to Grade 0-1 within 12 weeks of the last dose.

Dosing interruptions are permitted in the case of medical / surgical events or logistical reasons not related to study therapy (e.g., elective surgery, unrelated medical events, patient vacation, and/or holidays). Subjects should be placed back on study therapy within 3 weeks of the scheduled interruption, unless otherwise discussed with the Sponsor. The reason for interruption should be documented in the patient's study record.

In case toxicity does not resolve to Grade 0-1 or baseline within 12 weeks after last infusion, trial treatment will be discontinued. Subjects with a laboratory adverse event still at Grade 2 after 12 weeks may continue treatment in the trial only if asymptomatic and controlled.

Subjects who experience a recurrence of the same severe or life-threatening event at the same grade or greater with re-challenge of MK-3475 will be discontinued from trial treatment.

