9.0 DATA MANAGEMENT

Data collected from the study will be entered in REDCap database. The Principal Investigator is responsible for assuring that the data entered into the database are complete and accurate and that data entry is performed in a timely manner. Deidentified data will be shared with University of Hawaii Cancer Center (UHCC) for review and analysis.

9.1 Data collection for this study including:

- 1) demographic information (sex, race, and date of birth),

- 2) date of initial breast cancer diagnosis, pathology report of primary breast cancer, biomarker status, and date and location of distant metastases;
- 3) history of breast cancer surgery, and radiation therapy, if applicable;
- 4) date and type of chemotherapy and/or hormonal therapy for metastatic disease;
- 5) all AEs will be collected, however only ≥ 2 non-hematologic AEs and ≥ 3 hematological AEs will be recorded. Other abnormal laboratory values will not be reported as AEs; however, any clinical consequences of abnormality should be reported as AEs.
- 6) Concomitant medication will be recorded per standard of care in clinic database, and will not be recorded in the study database.

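### Section 6.3.1 excludes all abnormal laboratory values from AE reporting, against its own text, Table 2 and 9.1, so asymptomatic graded laboratory toxicity could go unrecorded

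*Combined protocol and SAP*

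**What the plan says.** Section 6.3.1 gives three instructions on recording.

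1. "Unexpected adverse events including laboratory adverse events deemed clinically significant by the investigator will be graded and recorded".
2. AEs at or above 2 (non-hematological) and 3 (hematological), attributed to the drug or not, "will be documented in the medical record and recorded in REDCap database". The numbers appear without the word grade, but the surrounding CTCAE text makes that the evident meaning.
3. "Abnormal laboratory values will not be reported as AEs", although their clinical consequences are to be reported.

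Section 9.1 repeats the two thresholds and then says "Other abnormal laboratory values will not be reported as AEs", again with clinical consequences to be reported. Its exclusion starts with a word that 6.3.1 does not have.

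Section 4.2.2 treats graded laboratory findings as adverse events. Table 2 is titled as guidance for drug-related adverse events. Its row "AST, ALT, or Increased Bilirubin" leads to a hold at Grade 2 and to permanent discontinuation at Grades 3-4, with a footnote for some patients with liver metastasis. The text after the table says "Subjects with a laboratory adverse event still at Grade 2 after 12 weeks may continue treatment", on condition that the finding is controlled and without symptoms.

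**The concern.** The third instruction in 6.3.1 has no exception, and it cannot be followed together with the other two. Hematological AEs of Grade 3 or higher are largely cytopenias, that is, laboratory values. If abnormal laboratory values are never AEs, that category is nearly empty and the laboratory AEs in the first instruction do not exist.

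At stake is whether the study database shows toxicity that the protocol itself considers important enough to interrupt or end treatment. Blood counts, chemistry and thyroid tests are scheduled throughout treatment (section 5.0), so these abnormalities will be seen. The open question is whether they are recorded as AEs. Two staff members could each follow the protocol and handle the same event differently. The first exploratory objective (section 2.2) relates biomarkers to safety, and inconsistent capture would misclassify that outcome.

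**Working it through.** The plan states no figure on this point, and no arithmetic applies. The check is to take example events through each section.

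| Event | 6.3.1 exclusion, literal | 9.1, 'other' read as below threshold | 4.2.2 |
|---|---|---|---|
| Isolated Grade 2 ALT rise, no symptoms, drug-related | Not recorded | Recorded | Hold |
| Isolated Grade 3 ALT rise, no symptoms, drug-related | Not recorded | Recorded | Permanent discontinuation, subject to the footnote |
| Grade 3 cytopenia, no clinical consequence, drug-related | Not recorded | Recorded | Hold, under the row for all other toxicity |
| Grade 1 laboratory change, no consequence | Not recorded | Not recorded | No action |

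The first three rows show the conflict: two sections of one protocol give opposite answers, and in each case 4.2.2 changes treatment.

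Next, do the other provisions recover those three events if 6.3.1 is taken literally?

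- **Clinical consequences.** An ALT rise or cytopenia without symptoms may have none, and the protocol does not say whether a hold counts as one.
- **Clinically significant laboratory AEs.** The sentence covers unexpected events. Liver-test changes are anticipated in Table 2 and section 4.4, so they may fall outside it. Where it does apply, it contradicts the exclusion in the same section.
- **Events of clinical interest (6.3.2.3).** The hepatic criterion needs AST or ALT at 3 times the upper limit or more, bilirubin at 2 times or more and alkaline phosphatase below 2 times, all together. An isolated ALT rise or a cytopenia does not meet it.
- **Serious adverse events (6.3.2.1).** An event that needs intervention may be reported as an important medical event, but this rests on judgment.
- **Other data items.** The list in 9.1 has no item for laboratory results and keeps concomitant medication out of the study database. Steroids given for a liver-test rise would therefore leave no trace there. The list may not be exhaustive, so this shows only that no alternative capture is stated.

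Finally, what does the gap affect? Section 7.0 bases the primary endpoint on disease control, so both Simon designs (12 then 35 patients; 21 then 50) are untouched. Its toxicity stopping rule counts only events that are serious, unexpected and related, so it is affected only if a laboratory event meets all three conditions. Section 7.0 specifies no AE incidence table. The effect falls on the recorded safety data and on whatever uses them, including the biomarker-safety analysis.

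**The case against.** The strongest defence is that 9.1, the data-collection section, already settles the matter. It gives the thresholds and then excludes the other abnormal values, which reads naturally as those below the thresholds. Section 6.3.1 has the same order and lacks only that word, and its hematological category makes little sense on any other reading. Sensible staff would harmonise the two sections, and nothing would be lost. This stands as far as it goes: an undercount is possible, not certain. But 6.3.1 is the section on AE assessment and its exclusion is unqualified, while 9.1 does not say what its values are other than. The protocol should not depend on staff choosing the better reading.

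It is also true that the exclusion sentence goes on to require reporting of clinical consequences, and that Table 2 can be applied from the medical record, so dosing does not depend on an AE entry. The loss would be in the study data.

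Three stronger readings are tempting, and the documents do not support them.

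- A reader might infer that laboratory toxicity *will* be undercounted. That follows only from the literal reading of 6.3.1.
- A reader might infer that half of Table 2 is lost, because five of its ten rows (liver tests, hyperglycemia, hyperthyroidism, hypothyroidism, renal) are detected mainly by blood tests. Only the liver-test row is defined purely by laboratory values. The others name conditions, or tie the laboratory finding to one, and a diagnosed condition is more than an abnormal value.
- A reader might size the problem with a zero-event limit: 1 - 0.05^(1/50) = 5.8% for 50 patients, or 1 - 0.05^(1/35) = 8.2% for 35. The arithmetic is right, but it describes how a count of zero would be read. It does not measure how many events are missed.

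**Conclusion.** The contradiction is real, both within 6.3.1 and between it and 4.2.2 and 9.1. If 6.3.1 is followed literally, non-hematologic laboratory toxicity of Grade 2 or higher and hematologic toxicity of Grade 3 or higher could stay out of the AE data when there are no symptoms, even if treatment was held or stopped because of it. The remaining reporting routes are too narrow or too discretionary to recover it reliably.

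The conclusion assumes that at least some staff apply the 6.3.1 exclusion as written. If all apply 9.1 with 'other' meaning below threshold, nothing above the thresholds is lost. The size of any undercount cannot be derived, because the documents give neither an expected rate of laboratory toxicity nor an AE count. The efficacy conclusion is not at risk. What is at risk is the completeness and consistency of the toxicity record, which justifies a correction at this low cost.

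**What to change.** Put one identical recording rule in 6.3.1 and 9.1, for example:

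> A laboratory abnormality is recorded as an AE if it meets the recording threshold (Grade ≥2 non-hematologic, Grade ≥3 hematologic) or leads to a hold or discontinuation under Table 2. All other laboratory findings stay out of the AE record, but any clinical consequences they have are reported.

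Adding the word 'other' to 6.3.1 would align the two sections but still leave open what it refers to. The Table 2 clause is not redundant. Its footnotes allow a hold for a persistent Grade 2 drug-related event, which for a hematologic finding lies below the recording threshold. They also set a liver-test criterion relative to baseline and not to a grade.

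The cost is one rule in two sections, a little more data entry and possibly higher reported AE counts. No dose or management rule changes. If patients have already been treated, the AE records should be checked against laboratory results and treatment holds for events left out under the present wording.
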